5.3 Subject Withdrawal

- 5.3.1 Given the short nature of the treatment regimen (radiation is given over 1.5-2 weeks), and very low rates of toxicity during radiation treatment, it is unlikely that patients will withdraw from the study once radiation treatment has begun. However, subjects have the right to withdraw from the study at any time.
- 5.3.2 Subjects may be withdrawn from the study if a subject's status declines and in the opinion of the treating physicians it is in the subject's best interest to be withdrawn. Subjects may also be withdrawn if there is a violation of the protocol inclusion and exclusion criteria as deemed relevant by the treating physician and the principal investigator.
- 5.3.3 It is anticipated that the most likely reason for a subject withdrawal will be for those not suitable for APBI based on radiation treatment planning (see Section 6.4 and 6.4.2 below for further details). As these patients would be withdrawn prior to delivery of study related treatment, they will then be replaced on the study and not counted toward the total accrual goal of 40 patients. Similarly, patients withdrawing for any other reason prior to delivery of treatment will be replaced on the study and not counted toward the total accrual goal.
- 5.3.4 In the rare case that a patient withdraws from the protocol after the initiation of treatment, only data collected up until the date of withdrawal will be used in analysis. If the withdrawal occurs during radiation therapy, data will only be included in analysis of the primary study endpoint if a post-operative complication occurs.
- 5.3.5 Patients who withdraw from the study should be treated in accordance with normal standards of care. Follow-up will be per the discretion of the patient's treating physicians, but at a minimum be in accordance with NCCN guidelines.

Management of disease recurrence or any unforeseen late morbidity of treatment will be managed by the treating physicians.

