11.0 Statistical Considerations

11.1 Sample Size, Power Calculations, and Comparison of Post-Operative Complications to Historical Controls

The primary endpoint of this study will be post-operative complications (as defined in section 10.1.4). The complication rate measured on this study will be compared to a historical control of 32% of patients, as outlined in section 1.6. This will be measured on an individual patient level. Hence a surgical complication rate that exceeds 31% will be considered unacceptable and result in a negative study. A post-op complication rate of 14% or less will be considered a successful demonstration of the safety of this treatment. This number was selected because it is roughly half the complication rate observed on the study by Horton et.al. (94) and represents an increase in complication rate of only 8% over that reported by Boostrom et.al. (102). To demonstrate this, a Simon's two stage design (104) will be used for this study. The value of this approach is that in stage 1 it can be demonstrated that pre-operative APBI using this dose and fractionation scheme is not excessively risky. Once that condition is satisfied, stage 2 is then used to demonstrate that it meets a better standard of complications compared to the Horton study with only a modest increase in complications when compared with historical series of complications observed without pre-operative radiation therapy.

For this analysis we assume as a null hypothesis that the true complication rate is 0.31. This will be tested against a one-sided alternative. In stage one of accrual, 17 patients will be enrolled. If there are 5 or more complications in these 17 patients, enrollment will be suspended and the study will be evaluated for possible closure. This will serve as the stopping rules for the study under the null hypothesis of a 31% complication rate. Otherwise, 22 additional patients will be accrued (total 39) in stage two, and the null hypothesis will be rejected if there are 7 or fewer complications among the 39 total. This design yields a type I error rate of approximately 0.05 and power of 0.80 when the true complication rate is 14%. With this design, the probability of stopping early is 0.6453. To allow for possible withdrawal prior start of treatment or other unforeseen problem with enrollment, total enrollment will be 40 patients.

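### The limits of 5 in 17 and 7 in 39 count enrolled patients, and a treated patient with no observable 3-month post-operative window is neither replaced nor defined, so each such loss favours a safety claim

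*Combined protocol and SAP*

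**What the plan says.** Both looks in section 11.1 are defined on recruited patients. The condition for pausing the trial at stage one reads: "In stage one of accrual, 17 patients will be enrolled. If there are 5 or more complications in these 17 patients". If that condition is not met, stage two adds 22 patients, again counted as they are accrued. The final rule is stated on all of them: "the null hypothesis will be rejected if there are 7 or fewer complications among the 39 total". The null rate is fixed there too: "we assume as a null hypothesis that the true complication rate is 0.31". The section states a type I error of about 0.05, power of 0.80 at a true rate of 14%, and an early stopping probability of 0.6453. Enrollment is set at 40, one above the design's 39, to cover withdrawal before treatment or an unforeseen enrollment problem.

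Four other sections determine who can contribute an event:

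- Section 10.1.4 limits the primary endpoint to complications within 3 months of surgery.
- Section 8.1 places surgery 5 to 8 weeks after radiation ends.
- Section 5.3.3 first replaces patients found unsuitable at treatment planning, then adds that "patients withdrawing for any other reason prior to delivery of treatment will be replaced on the study". Replacement therefore stops once treatment is delivered.
- Section 5.3.2 allows physicians to withdraw a patient whose "status declines and in the opinion of the treating physicians it is in the" interest of that patient, and also for eligibility violations. Under 5.3.4, data after the withdrawal date are not used. A patient who withdraws during radiation enters the primary analysis only if she has a post-operative complication.

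No section defines an evaluable population, covers a patient who stays on study without surgery, or says how an incomplete 3-month window is counted.

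**The concern.** The limits 4 and 7 were derived for 17 and 39 patients who can each have an observed complication. A treated patient with no surgery cannot have one. A patient who leaves early can have one only up to the day she leaves. With the limits fixed, every such patient lowers the expected number of complications without lowering the number that counts as success.

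The error therefore runs in one direction, toward declaring the regimen safe. In a single-arm safety trial of 39 patients it affects both the claim at the end and the stage one stop that protects later patients. Withdrawal under 5.3.2 adds to this: a patient withdrawn because she is deteriorating may be one whose complication is still to come, and 5.3.4 then closes her record.

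**Working it through.** **Inputs.** From 11.1: 17 patients in stage one, continue at 4 or fewer complications; 22 more in stage two, claim safety at 7 or fewer of 39; null rate 0.31; historical control 0.32; alternative 0.14. Assumption: one or two treated patients have no observable post-operative window. The documents give no loss rate.

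**Formula.** With a evaluable patients in stage one and b in stage two,

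P(claim safety | p) = Σ over x = 0 to 4 of P[Bin(a, p) = x] × P[Bin(b, p) ≤ 7 − x].

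P(early stop | p) = P[Bin(a, p) ≥ 5].

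**Step 1: the plan's own figures (a = 17, b = 22, p = 0.31).**

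| x | P[Bin(17) = x] | P[Bin(22) ≤ 7 − x] | product |
|---|---|---|---|
| 0 | 0.0018 | 0.6327 | 0.00115 |
| 1 | 0.0139 | 0.4532 | 0.00631 |
| 2 | 0.0500 | 0.2784 | 0.01392 |
| 3 | 0.1123 | 0.1411 | 0.01585 |
| 4 | 0.1766 | 0.0562 | 0.00992 |

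The products sum to 0.0471. Early stopping is 0.6453, and at p = 0.14 the power is 0.805. All three agree with 11.1. The margin below 0.05 is 0.05 − 0.0471 = 0.0029.

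**Step 2: remove evaluable patients, keep the limits.** A patient scored event-free with no window adds zero to the count, so 17 or 22 falls by one and the limits stay at 4 and 7. Dropping her without replacement gives the same a, b and limits, hence the same error. For one loss in stage one (a = 16, b = 22) the products are 0.00167 + 0.00860 + 0.01780 + 0.01891 + 0.01100 = 0.0580.

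| Losses (stage 1, stage 2) | Type I error at 0.31 | Type I error at 0.32 | Early stop at 0.31 |
|---|---|---|---|
| 0, 0 | 0.0471 | 0.0358 | 0.6453 |
| 0, 1 | 0.0567 | 0.0436 | 0.6453 |
| 1, 0 | 0.0580 | 0.0447 | 0.5846 |
| 0, 2 | 0.0677 | 0.0528 | 0.6453 |
| 1, 1 | 0.0695 | 0.0542 | 0.5846 |
| 2, 0 | 0.0709 | 0.0554 | 0.5187 |

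One loss adds 0.0567 − 0.0471 = 0.0096 to 0.0580 − 0.0471 = 0.0109, about one percentage point. A patient whose window is only partly observed adds less than a full loss, so these figures are upper values for her.

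**Step 3: the opposite convention.** Counting one lost patient as a complication lowers the number of further complications allowed. If she is in stage one, the limits become 3 and 6 with a = 16, b = 22: type I error 0.023, power 0.670. If she is in stage two, the final limit becomes 6 with a = 17, b = 21: type I error 0.026, power 0.712. Against a designed power of 0.805, this suits a sensitivity analysis and not the primary rule.

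**The case against.** The strongest reply is that the plan expects almost no such patients. Section 5.3.4 calls withdrawal after treatment starts rare, 3.1.1 admits only women planning breast-conserving surgery, and the operation is part of their cancer treatment. One loss moves the error by about a point against a stated value of approximately 0.05, and against the 32% control it stays below 0.05. The 40th patient could absorb one loss. All of this stands as a limit on size. However, 11.1 does not name loss after radiation as that patient's purpose or make her a replacement, and she gives no spare for the stage one look.

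A reader might infer that the plan scores unoperated patients as complication-free. No sentence says so, and the rule in 5.3.4 for withdrawal during radiation leaves event-free patients out. That corrects the description but not the arithmetic, because leaving a patient out while keeping the limits gives the same error. Nor does enrolled mean everyone who signs up: with 5.3.3, the 17 and 39 are in effect patients who started treatment.

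A reader might also infer that withdrawal for decline routinely hides complications. The documents do not support that. Data up to withdrawal are used, so a complication already recorded still counts; only later events are lost.

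**Conclusion.** The concern holds as a gap in the denominator with a known direction. Sections 11.1, 10.1.4, 5.3.3 and 5.3.4 together leave treated but non-evaluable patients unreplaced under fixed limits, and this can only make a safety claim easier.

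The size is modest and conditional. Assuming one patient with no observable window, the type I error at 31% is 0.057-0.058 instead of 0.047; assuming two, 0.068-0.071. One loss in stage one cuts the chance of stopping early under the null from 0.645 to 0.585. Against 32% the error is 0.044-0.045 with one loss and 0.053-0.055 with two. A reader might infer a gross loss of error control, but that would need a loss rate the documents neither give nor suggest. The change is still worth making, because the design's margin below 0.05 is only 0.003 and the remedy is mainly wording.

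**What to change.** 1. **Section 11.1.** Define the 17 and the 39 as patients who had the post-radiation breast operation and either completed the 3-month window or already had a complication. Having had the operation is not enough on its own, since a patient can leave after it. Replace treated patients who are not evaluable, using the planned 40th patient first, and list them with reasons. Report a sensitivity analysis that counts them as complications. If fewer than 39 are evaluable at the end, report the exact type I error for the number achieved. With 17 and 39 evaluable patients, the stated 0.047, 0.805 and 0.6453 apply unchanged.

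2. **Sections 5.3.2 and 5.3.4.** State that physician-initiated withdrawal, for decline or for an eligibility violation, does not end data collection. All treated patients are followed for complications, recurrence and survival unless consent is withdrawn.

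**Cost.** Possibly one or two replacement patients and some added follow-up. Under assumed loss rates, 39/(1 − 0.025) = 40, which the planned enrollment covers, and 39/(1 − 0.05) = 41.05, so 42. Each look also has to wait until its patients are evaluable.

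### Section 11.1 has no stage 2 rule tied to the primary endpoint: after an 8th complication success is impossible, and whether accrual stops is left to DSMC discretion

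*Combined protocol and SAP*

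**What the plan says.** Section 11.1 uses a Simon two-stage design: "we assume as a null hypothesis that the true complication rate is 0.31", and "This will be tested against a one-sided alternative". For stage 1, "In stage one of accrual, 17 patients will be enrolled", and "If there are 5 or more complications in these 17 patients, enrollment will be suspended and the study will be evaluated for possible closure". The section presents this as the stopping rule for the study. If stage 1 is passed, "22 additional patients will be accrued (total 39) in stage two". The criterion for success at the end of the trial is that "the null hypothesis will be rejected if there are 7 or fewer complications among the 39 total". It gives no complication count at which stage 2 accrual would pause.

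Oversight outside 11.1 does continue. Under sections 10.4.1 and 10.4.2 the DSMC reviews reports twice a year, or more often if needed. It may recommend suspension or termination, and it may terminate the study if it judges it unsafe. The events it reviews individually are unexpected grade 3, all grade 4 and 5, and any others that need expedited reporting. Section 10.1.4 counts infection, dehiscence, drained hematoma and symptomatic seroma toward the primary endpoint from CTCAE grade 2.

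**The concern.** The primary endpoint is safety, so the events that decide the trial are harms to its patients. Once 8 patients have had a complication, the success criterion cannot be met whatever happens to the rest, yet the written default is to go on to 39. The sponsor already accepts suspend-and-review on a complication count in stage 1. Stage 2 has no equivalent, and nothing in the plan tells the DSMC that the deciding count has been reached. Section 1.6 expects infection and symptomatic seroma to be the most common complications. Eight grade 2 events of that kind could accumulate between scheduled reports without any one of them being reviewed individually. At stake is the enrollment of further patients, without a prompted review, after the 14% claim can no longer succeed.

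**Working it through.** **Inputs from section 11.1.** Null rate 0.31; target rate 0.14; stage 1 of 17 patients, continue with 4 or fewer complications; total 39, success with 7 or fewer. X1 and X2 are the complication counts among the first 17 and the next 22 patients.

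**The plan's own figures.** Five or more of 17 is treated as closure, as the stated figures imply.
- Early stopping = P(X1 ≥ 5 | 17, 0.31) = 0.6453. The plan says "the probability of stopping early is 0.6453".
- P(success) = Σ(x = 0 to 4) P(X1 = x) · P(X2 ≤ 7 − x | 22, p).
- At p = 0.31 the five terms are 0.0012 + 0.0063 + 0.0139 + 0.0158 + 0.0099 = 0.0471, the type I error.
- At p = 0.14 they are 0.0764 + 0.2075 + 0.2563 + 0.1840 + 0.0809 = 0.8050 (before rounding of the terms), the power.

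The plan states "This design yields a type I error rate of approximately 0.05 and power of 0.80 when the true complication rate is 14" percent. Its figures reproduce.

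**Earliest point of no return.** Four complications in stage 1, then four in a row, puts the 8th at patient 17 + 4 = 21, with 39 − 21 = 18 still to come.

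**How often the 8th event is reached.** A trial that enters stage 2 either succeeds or reaches 8, so P(reached) = P(X1 ≤ 4) − P(success).

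| True rate | Enters stage 2 | Success | Reaches 8th, all trials | Reaches 8th, given stage 2 |
|---|---|---|---|---|
| 31% | 0.3547 | 0.0471 | 0.3075 | 0.867 |
| 25% | 0.5739 | 0.1919 | 0.3820 | 0.666 |
| 14% | 0.9222 | 0.8050 | 0.1172 | 0.127 |

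**Patients still to enroll at that moment.** With m = i − 17, the probability that the 8th event falls at patient i is Σ(x = 0 to 4) P(X1 = x) · C(m − 1, 7 − x) · p^(8 − x) · (1 − p)^(m − 8 + x). Averaging 39 − i over this distribution gives 8.6 patients at 31%, 7.0 at 25% and 4.6 at 14%. Stopping there would lower the expected sample size from 24.8 to 22.2 at 31%, and from 37.3 to 36.7 at 14%. These are upper bounds, because they assume that each outcome is known before the next patient enrolls.

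**Allowing for the lag.** The documents give no accrual rate, so one and two patients per month are assumptions. The lag was simulated as 0.5 to 2 months from enrollment to radiation (6.5.1: generally within 60 days), half a month of treatment (6.5.5), 5 to 8 weeks to surgery (8.1), and a complication at a uniformly distributed time in the 3-month window (10.1.4). At a true 31%, given that the 8th event occurs, the mean number still to enroll is 4.8 at one per month and 1.7 at two per month. Nobody is left in 22% and 56% of those trials respectively. With a fixed lag of 3 to 6 months instead, the means run from 5.8 down to 3.4 at one per month, and from 3.4 down to 0.5 at two per month.

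**What the 8th event says about the rate.** 8/39 = 20.5%, and 8/26 = 30.8%. An 8th event at patient 26 or later therefore comes with an observed rate below 31%. Of the trials that reach an 8th event, this is so in 85% at a true 31%, 92% at 25% and 98% at 14%.

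**The case against.** The case against has five parts.

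- **Accrual need not continue.** A reader might infer that enrollment must run to 39 after the 8th event. Sections 10.4.1 and 10.4.2 do not support that, because the DSMC can meet more often than twice a year and can suspend or terminate. This stands: what is missing is a prespecified trigger, not oversight.
- **The design is standard.** A Simon design decides at the end of each stage, and curtailment within a stage is optional. This stands: the design is sound and its stated properties are correct.
- **Eight events are not a safety failure.** A reader might take the 8th event as proof that the regimen exceeds 31%. Section 11.1 calls a rate above 31% unacceptable and 14% or less a success, and 8 of 39 lies between them. The 8th event is mainly a futility point for the 14% claim. It also occurs in 13% of stage 2 trials at the target rate itself.
- **Later patients still inform the primary objective.** Section 2.1 asks first for the complication rate. The test decision is fixed at the 8th event, but the estimate and its precision are not. This stands as a cost of closing early.
- **The saving is small once the lag is counted.** This stands in part: at two patients per month little may be saved.

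None of these removes the reason for a non-binding trigger. Discretion works better when the committee is told that the deciding count has been reached, and the individual-event review is not built to pick up grade 2 endpoint events.

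**Conclusion.** The point holds as a gap in prespecification. Section 11.1 names no action at the 8th complication, although from then on the null cannot be rejected. The gap would matter in 31% of all trials at a true rate of 31%, 38% at 25% and 12% at 14%. At 31% the mean number of patients still to enroll is at most 8.6, and more plausibly about 5 at one per month or under 2 at two per month. The lag-adjusted figures rest on the assumed accrual rates and timing; the others assume independent outcomes with a constant complication rate. It is not a mistake in the Simon design, and the documents do not support reading it as unchecked enrollment into a regimen already shown to be unsafe. It is a cheap improvement, worth making because the endpoint is harm to patients.

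**What to change.** Add one sentence to 11.1: when the 8th patient with a primary-endpoint complication is confirmed, at any time in stage 2, the DSMC is notified, enrollment is suspended and the study is evaluated for possible closure, as in stage 1. Make it non-binding, so that the committee can weigh the secondary objectives. Type I error (0.047) and power (0.805) do not change whether or not accrual resumes, because success is already ruled out.

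The rule requires a running count of affected patients, including grade 2 events, to be kept and reported to the DSMC. If the committee closes the trial, fewer patients remain for the secondary endpoints in 11.2, and the complication rate is estimated less precisely. The simple proportion would also be biased upward, because accrual would have ended on an event. Section 11.1 should therefore add that the rate will then be reported with an estimator and interval that allow for the stopping rule.

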Patient Population: (See Section 3.0 for Eligibility and additional requirements Stage I-IIA, Node negative breast cancer eligible for breast conservation.

Required Sample Size: 40

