Sample size for Simon's Two-Stage Design was calculated using a web-based calculator (retrieved February 11, 2016) (106).

In 2012-2013, 586 new cases of invasive breast cancer were seen at FH. This included 424 patients who had stage I and IIA disease, the population targeted in this proposal. We estimate that 60-70% of these patients would be eligible for screening, with 30-40% eligible for the study. This will allow for an adequate pool of patients for the targeted enrollment of 40 patients.

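### Does enrolling 40 patients against a final rule written for 39 leave the primary test undefined?

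*Combined protocol and SAP*

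**What the plan says.** Section 11.1 describes a Simon two-stage design with a null complication rate of 31% and an alternative of 14%. Stage 1 has 17 patients, and 5 or more complications suspend enrolment. If the trial goes on, the plan is that "22 additional patients will be accrued (total 39) in stage two". The final criterion is written for that same denominator: "the null hypothesis will be rejected if there are 7 or fewer complications among the 39 total". The stated properties are a type I error of about 0.05, power of 0.80 and an early-stopping probability of 0.6453.

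The same section then sets the enrolment figure: "To allow for possible withdrawal prior start of treatment or other unforeseen problem with enrollment, total enrollment will be 40 patients". The front summary ("Required Sample Size: 40") and the accrual paragraph of 11.1 ("targeted enrollment of 40 patients") repeat the 40.

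Section 5.3.3 deals with withdrawal before treatment. Patients found unsuitable at radiation planning are covered by "they will then be replaced on the study and not counted toward the total accrual goal of 40 patients", and the next sentence extends this: "patients withdrawing for any other reason prior to delivery of treatment will be replaced on the study and not counted". Section 5.3.4 deals with withdrawal during radiation, where "data will only be included in analysis of the primary study endpoint if a post-operative complication occurs".

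**The concern.** Section 11.1 gives two reasons for the 40th place, and 5.3.3 removes the first of them: a patient lost before treatment is replaced and never uses a place. The goal is then 40 patients who have started treatment. Section 5.3.1 expects few to withdraw after that, so a completed trial could well have 40 evaluable patients facing a rule whose denominator is 39.

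If so, one total is not settled. With 8 complications in 40, setting aside a patient who had a complication leaves 7 of 39 and the null is rejected. Setting aside a patient who had none leaves 8 of 39 and it is not. The 14% and 31% benchmarks in 11.1 do not help, because 8/40 = 20% lies between them. The trial is single-arm and unblinded, so the choice could in principle be made with outcomes known, at the boundary of its only formal primary test.

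**Working it through.** **Inputs (section 11.1).** Null rate 0.31; alternative 0.14; stage 1 n = 17, continue at 4 or fewer; final n = 39, reject at 7 or fewer; enrolment 40. The stage 1 stop is treated as binding.

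**1. The plan's own figures.** With b(n, x, p) the binomial probability:
- P(stop early) = P(Bin(17, p) ≥ 5) = 0.6453 at p = 0.31, matching the plan, and 0.0778 at p = 0.14.
- P(reject) = Σ over x = 0..4 of b(17, x, p) × P(Bin(22, p) ≤ 7 − x) = 0.0471 at 0.31 and 0.8050 at 0.14.

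The 39-patient design is correct as stated.

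**2. Which totals out of 40 are open?**
- 7 or fewer of 40: any 39 of them contain at most 7, so the null is rejected.
- 9 or more of 40: any 39 contain at least 8, so it is not rejected.
- Exactly 8 of 40: depends on the patient set aside.

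**3. How likely is exactly 8 of 40 with stage 1 passed?** The number of arrangements is Σ over x = 0..4 of C(17, x) × C(23, 8 − x):

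490,314 + 4,167,669 + 13,728,792 + 22,881,320 + 21,074,900 = 62,342,995.

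- At 0.14: 62,342,995 × 0.14^8 × 0.86^32 = 0.0738.
- At 0.31: 62,342,995 × 0.31^8 × 0.69^32 = 0.0371.
- For other assumed true rates: 2.1% at 10%, 12.6% at 20%, 9.6% at 25%.

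**4. If the 40th patient is the spare.** Arrangements with 7 complications in the first 39, stage 1 passed and a complication in the 40th: Σ over x = 0..4 of C(17, x) × C(22, 7 − x) = 13,659,789. The share is 13,659,789 / 62,342,995 = 0.219, whatever the true rate.
- Rejected at 7 of 39: 0.219 × 0.0738 = 0.0162 at 0.14; 0.219 × 0.0371 = 0.0081 at 0.31.
- Not rejected at 8 of 39: 0.0576 and 0.0289.

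**5. Error rates under each way of handling 40 evaluable patients.**

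| Handling | Type I error (0.31) | Power (0.14) |
|---|---|---|
| First 39 tested, 7 or fewer | 0.0471 | 0.8050 |
| All 40 tested, 7 or fewer | 0.0390 | 0.7888 |
| All 40 tested, 8 or fewer | 0.0761 | 0.8626 |

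The first two rows differ by 0.8050 − 0.7888 = 0.0162 and 0.0471 − 0.0390 = 0.0081. These are the step 4 figures, so the two readings that keep the written cut-off disagree only there.

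**6. Allowing for loss after treatment starts.** The documents give no rate, so I assume independent losses of 1%, 2% or 5% per patient. All 40 are then evaluable with probability 0.99^40 = 0.67, 0.98^40 = 0.45 or 0.95^40 = 0.13. At a true rate of 14% the 7.4% becomes about 4.9%, 3.3% or 0.9%, and the 1.6% becomes about 1.1%, 0.7% or 0.2%.

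**The case for a change.** The best case for a change is that the ambiguity sits on the decision boundary of the primary safety test and one sentence would remove it. Even the natural reading leaves the order open: registration, first fraction and surgery could each pick a different 39th patient, since treatment may start up to about 60 days after enrolment (6.5.1) and surgery falls 5 to 8 weeks after radiation (8.1). If someone always set aside a patient with a complication, the procedure would amount to allowing 8 of 40, with type I error 0.039 + 0.037 = 0.076.

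Part of this stands. The rule for a surplus patient is unwritten, and the first reason given for the 40th place overlaps with 5.3.3. The worst case does not carry far, however. It needs a patient to be removed because she had a complication, and nothing in the plan permits that. Any order fixed without regard to outcome has the same operating characteristics as the first row of the table.

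Nor is the 40th place idle. The second reason in 11.1 remains, and under 5.3.4 one withdrawal during radiation without a complication brings 40 down to the 39 that the rule expects. Cutting the target to 39 would therefore be worse: 5.3.3 replaces only pre-treatment withdrawals, so one such loss would leave 38 and no rule.

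**Conclusion.** No change is needed. Section 11.1 contains one decision rule with one denominator and mentions the 40th patient only as an allowance, so the ordinary reading is 39 tested and one spare, with any 40th evaluable patient reported alongside. That reading delivers the stated properties (0.047 and 0.805). The stricter reading, 7 or fewer among all 40, is also safe on type I error (0.039) and gives up 1.6 points of power. The two differ in 1.6% of trials at a true rate of 14% and 0.8% at 31%, and less often if any patient is lost after starting treatment. The overlap with 5.3.3 is a loose explanation of the spare place and alters no result.

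This rests on three assumptions: the stage 1 stop is binding, all 40 patients are evaluable (the least favourable case for the plan), and the spare is identified by order and not by outcome. It is a missing detail that a competent analyst would settle correctly from the existing text.
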